Participant Safety	There remains the risk that a Participant may not identify a skin lesion on their body that is malignant (both a PSLC and a non-PSLC). However, all risks are associated with the current at-home standard of care protocol for SSEs and not increased by use of the Sklip System. All Participants are required to come for an in-person FBSE, regardless of if they identify a PSLC during the At-home Phase. The FBSE will ensure that no malignancies are missed.
Synopsis of Statistical Analysis	
An intent-to-treat (ITT) analysis set will include those who are enrolled in the Study regardless of adherence. All primary analyses will be conducted using the intent-to-treat analysis set. Demographic and clinical characteristics will be summarized using descriptive statistics (e.g. proportions, mean/median, and standard deviation/range).
 
The Ground Truth will be the combination of the following:
 
Dataset N) DDI dermoscopic diagnosis ground truth (DDI-GT) for PSLCs that were not biopsied during the In-Person Phase, and

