**Without dermatology Provider present,**

**with Study Coordinator present:**

The Participant will be asked to provide their Participant Mole Log Sheet (PMLS). Then, all PSLCs recorded in the PMLS will entered into REDCap Cloud by the Study Coordinator. Any Participant-selected PSLCs that match those identified earlier as SUSPICIOUS by the DP will be marked with a horizontal line one (1) inch away from the target PSLC using a green surgical marker. Therefore, PSLCs identified by both the DP and Participant will have a plus symbol. Next, the Study Coordinator will take and record (near-perfect) SCI and DDI for all PSLCs recorded in the PMLS and those PSLCs identified by the DP as SUSPICIOUS (not matching the Participant PSLCs). Then, the Study Coordinator will complete the following:

- 1) Take one (1) photo of the Participant identification sticker with a Study Site secure smartphone/tablet
- 2) Take one (1) smartphone clinical image (SCI) of each target PSLC recorded in the Participant Mole Log Sheet (PMLS)
- 3) Take one (1) digital dermoscopy image (DDI) of each target PSLC using the Sklip dermatoscope.
- 4) Save the DDI of the target PSLC in the Study Site smartphone/tablet native photo gallery
- 5) Upload the Study Coordinator-taken DDI to the SMSA ("Scan Moles with Ai") within the Sklip App
- 6) Take one (1) screenshot the SMSA output
- 7) Record each SMSA output (SUSPICIOUS, UNREMARKABLE, ERROR) in REDCap Cloud, per target PSLC
- 8) If the Participant has taken a set of SCI/DDI at home of a PSLC that is not intended (qualified because of anatomic body site) for the Sklip System, the Study Coordinator should still capture a set of control SCI/DDI and upload to REDCap Cloud. The Participant standard clinical care will not be changed.
- 9) If the Participant took a set of SCI/DDI of a PSLC at home but did not follow instructions – specifically uploading the DDI to the Sklip System - the Study Coordinator should remind the Participant to complete this task in the patient room (using the DDI from their mobile device gallery), upload to the Sklip System, and record the output on their Mole Log Sheet. If this situation occurs, the Study Coordinator should make a note in

REDCap Cloud; If the Participant is/was concerned about a PSLC but did not take a set of SCI/DDI at home, this PSLC will not be included in the study.

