**Schedule for data collection:**

In order to avoid Participant PSLC recollection-bias, Study Coordinators will use the Participant Mole Log Sheet (PMLS) and Participant taken SCI/DDI for guidance and **record** the following Datasets in REDCap Cloud:

- A) Total number of PSLCs identified by the Participant at-home
- B) Total number of PSLCs identified by the DP in-office
- C) One (1) individual SMSA output recorded in the PMLS, per target PSLC (SUSPICIOUS, UNREMARKABLE and ERROR)

Ensuring that no PHI is shared, Study Coordinators will **export** the following from the Participant smartphone/tablet gallery titled “Moles” to the Study Site smartphone/tablet gallery via Bluetooth or secure email:

- D) One (1) Participant-taken SCI, per target PSLC
- E) One (1) Participant-taken DDI, per target PSLC
- F) One (1) Participant-taken SMSA output screenshot, per target PSLC

Then, Study Coordinators will **acquire** and **export** the following from the Study Site smartphone/tablet gallery to an OHSU secure cloud storage service:

- G) One (1) Study Coordinator-taken DDI (near-perfect image technical quality) for each PSLC recorded in the PMLS and suspicious PSLCs identified by the DP in-office that were not recorded in the PMLS

Then, Study Coordinators will **upload** the DDI in Dataset (G) to the SMSA on a Study Site smartphone/tablet and **record** the following Datasets into REDCap Cloud:

- H) One (1) Study Coordinator-taken SMSA output for each PSLC, recorded in the PMLS, using Dataset (G) (SUSPICIOUS, UNREMARKABLE and ERROR), including one (1) screenshots

Then, the Study Coordinator will **record** the following Datasets into REDCap Cloud:

- I) All other SCI of suspicious PSLCs identified by the DP in-office that were not recorded in the PMLS
- J) All other DDI of suspicious PSLCs identified by the DP in-office that were not recorded in the PMLS
- K) Pathology reports for all PSLCs that were biopsied during the In-Person Phase
- L) Number of adverse events reported during the Study

-----End of In-person Phase-----

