#### 8.1.2 DISEASE ASSESSMENT

All Participants will be required to obtain an in-person FBSE. Since PSLCs will be evaluated per standard clinical care pathways, the evaluating dermatology Provider may or may not be involved in the Study. The dermatology Provider will be blinded to Participant activity, including the Participant Mole Log Sheet. The dermatology Provider may choose to perform biopsy, when applicable, independent of Participant at-home findings.

Biopsies may be performed for suspicious lesions identified by the dermatology Provider during the FBSE and will be assessed by histologic assessment as part of current standards of care for diagnosis, independent of the Study. **The use of the Sklip System is for triage only and is not intended to act as a substitute for official diagnosis via pathology results, and all subsequent management and treatment of disease will be based off official histologic diagnosis and in accordance current guidelines.**

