#### 8.1.6 ADVERSE EVENT EVALUATION

The device does not pose a serious risk to the health, safety, or welfare of subjects. The clinical trial design is such that the potential risk of not flagging a suspicious lesion is appropriately mitigated and the trial itself does not pose a potential for serious risk to the health, safety, or welfare of a subject.

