## 8.10    **SCHEDULE OF EVENTS**

**Table 3. Schedule of events**

Days ( $\pm 3$ Days)	Recruitment	Enrollment	Data Entry	Phase 1 Survey
	Days -28 to -1	Day 1	Continuously	Day 42
Invite Participants	X			
Screening, Inclusion/exclusion criteria	X			
Informed Consent	X	X		
Onboard training		X		
MyChart, Direct message, Calls, Email, or Text	X	X		X
EMR Chart Review			X	X
Participant nPhase REDCap Cloud Survey	X	X		X

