### 10.5 TIME PERIOD AND FREQUENCY FOR EVENT ASSESSMENT AND FOLLOW-UP

The occurrence of an UP, AE or SAE may come to the attention of Study personnel during Study visits and interviews of a Study Participant presenting for medical care, upon review by a Study monitor, or during an audit. All AEs including local and systemic reactions not meeting the criteria for SAEs will be captured on the appropriate CRF. Information to be collected includes event description, time of onset, clinician's assessment of severity, seriousness, expectedness, relationship to Study product (assessed only by those with the training and authority to make a diagnosis), and date of resolution/stabilization of the event. All AEs occurring while on Study must be documented appropriately regardless of relationship. All AEs will be followed to adequate resolution.

Any medical condition that is present at the time that the Participant is screened will be considered as baseline and not reported as an AE. However, if the Study Participant's condition deteriorates at any time during the Study, it will

be recorded as an AE after enrollment. Changes in the severity of an AE will be documented to allow an assessment of the duration of the event at each level of severity to be performed. AEs characterized as intermittent require documentation of onset and duration of each episode. The Investigator will record all reportable events with start dates occurring any time after enrollment until the last day of Study participation. AEs will be evaluated using the current version of the [CTCAE v5.0](#). If a Participant electively schedules a follow up visit with a provider, the investigator will inquire about the occurrence of AE/SAEs. Events will be followed for outcome information until resolution or stabilization.

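### The only instruction to ask participants about adverse events is tied to an electively scheduled follow-up visit; as worded it does not cover the in-person exam that everyone must attend

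*Combined protocol and SAP*

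**What the plan says.** On asking about adverse events, Section 10.5 gives one instruction: "If a Participant electively schedules a follow up visit with a provider, the investigator will inquire about the occurrence of AE/SAEs". Otherwise, the same section says that events "may come to the attention of Study personnel during Study visits and interviews of a Study Participant presenting for medical care", or during monitoring or audit. It requires every event to be captured on a case report form, with start dates from enrollment to the last day of participation.

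The in-person exam is not elective. The Synopsis (Participant Safety) states "All Participants are required to come for an in-person FBSE, regardless of if they identify a PSLC during the At-home Phase", and Section 8.1.2 states "All Participants will be required to obtain an in-person FBSE".

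Other text on adverse events:

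- Section 10.1: onboarding teaches participants how to report psychological or behavioral effects, and the investigator is told at once if an event is reported.
- Section 3.1: charts are reviewed every 7 days, and the coordinator records "L) Number of adverse events reported during the Study".
- Section 10.4.3: psychological stress is the sole event of special interest.
- Section 11.4.4: adverse events are tabulated descriptively.

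**The concern.** If 10.5 is followed as written, the only people certain to be asked are those who choose to book a further visit. That is a self-selected group of unknown size. Everyone else contributes an event only if they volunteer it or it reaches the medical record.

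This matters most for the events the protocol expects. Section 10.2.1 lists stress from self-examination and changes in behavior. A participant may well not mention such effects unprompted, and a chart may not show them. A low or zero count in 11.4.4 could then mean that participants were asked and had nothing to report, or that they were never asked. The report would have no denominator to tell the two apart.

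**Working it through.** No figure in the plan depends on this point, so the check is a reading of each place where a question to all participants could stand.

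| Place | What it contains | Question on adverse events? |
|---|---|---|
| 3.1, provider steps at the exam | Skin exam, marking of lesions, skin phototype | No |
| 3.1, coordinator steps ("Then, the Study Coordinator will complete the following", nine items) | Images, algorithm outputs, handling of incomplete home tasks | No |
| 3.1, Dataset L | A count of events reported | No; a recording step |
| 8.1.6, Adverse Event Evaluation | A risk statement beginning "The device does not pose a serious risk to the health, safety, or welfare of subjects" | No; no procedure or timing |
| 8.10, schedule of events (seven rows) | Invitation, screening, consent, training, messages, chart review, and "Participant nPhase REDCap Cloud Survey" | No adverse event row and no column for the in-person visit |
| 6.1.8, end-of-study survey | Described as lesion counts | None described |
| Synopsis, post-survey | Content not stated | Unknown |
| 10.1, onboarding | How to report effects | No; spontaneous reporting |
| 10.5 | Inquiry at an electively scheduled follow-up visit | Yes, conditional |

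That gives one instruction to ask, which is conditional, and none at the mandatory exam.

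**Does the 10.5 sentence cover the exam?** The text points both ways.

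- *For:* Section 6.1.8 uses *follow up* for the required FBSE, and 5.3.1 uses it for the evaluation of all participants. Section 10.1 calls an optional provider evaluation an unscheduled visit and cites 8.9, yet 8.9 describes the in-person exam for all participants.
- *Against:* The Synopsis (Follow-up Duration) and 8.8 use *follow up* for care after the study. The word *electively* also does not fit an exam that the Synopsis and 8.1.2 make compulsory.

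The intention is therefore ambiguous. The wording, taken literally, excludes the exam.

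**What the number asked would mean.** This illustrates the role of the denominator and does not estimate the gap. With zero events among n participants asked, the one-sided 95% upper limit is 1 − 0.05^(1/n). From 11.2, the planned number before drop-out inflation is 423 ÷ 1.5 = 282.

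| Share asked (assumed) | n | Upper limit |
|---|---|---|
| 100% | 282 | 1.06% |
| 50% | 141 | 2.10% |
| 25% | 70 | 4.19% |
| 10% | 28 | 10.15% |

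The shares are assumptions; the documents give none. The calculation also counts unasked participants as giving no information, which ignores trained self-reporting and weekly chart review.

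**The case against.** The strongest reply is that 10.5 was meant to cover the exam. Sections 10.1 and 8.9 treat the in-person visit as an unscheduled visit, 6.1.8 and 5.3.1 use *follow up* for it, and participants without a booking schedule it themselves. On that reading the inquiry reaches everyone and the defect is one misplaced word. This stands as a plausible account of intent. It does not remove the need for a change, because site staff work from the text, and neither the exam steps nor the schedule of events tells them to ask.

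The other capture routes are also real. Participants are trained to report, charts are read weekly, and Dataset L and the case report forms give events a place to be recorded. A reader might infer that adverse events go uncollected, or that nobody is asked. The documents support neither. The gap is in active questioning, and forms outside the documents may already fill it. Section 12.2 defers monitoring details to a separate plan that is also not available.

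The argument is weaker for the event of special interest. Section 10.4.3 sets its threshold at a reported significant increase in stress together with a request for action. Mild stress that nobody mentions would not meet it, though a question might prompt some reports that would.

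Finally, the protocol declares the study non-significant risk, and the analysis methods in Section 11 use no adverse event count in a decision rule. Both limit the consequence.

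**Conclusion.** The point holds for the protocol text as worded. The sole instruction to ask is conditional on an elective visit, and no question is specified at the exam that all must attend. Ascertainment rests mainly on spontaneous reports, chart review and a count of reported events, unless the case report forms, survey forms or monitoring plan add a question.

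The size of the gap cannot be computed, because the documents do not say how many participants schedule an elective visit or provide for recording who was asked. A reader might take the 10.15% in the illustration as the trial's real uncertainty. It rests on an assumed 10% share and should not be used that way. A reader might also infer that 10.5 makes the exam optional. It does not: the Synopsis and 8.1.2 are explicit, and the conflicting sentence is in 10.1.

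The consequence is modest. It concerns the interpretation of a descriptive safety table and leaves the primary accuracy endpoints untouched. The change is still worth making because it is cheap and settles the ambiguity.

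**What to change.** 1. **Section 10.5.** Have the Study Coordinator ask every participant one fixed adverse event question, including stress from the self-exam, at the required in-person visit. Ask it after biopsy decisions are recorded, so that an answer cannot reveal at-home results to the blinded provider; the documents do not say whether biopsy comes before the coordinator's steps. Repeat the question in the day-42 survey. Record asked yes/no with Dataset L. Keep the elective-visit inquiry as an addition.
2. **Section 8.10.** Add an adverse event row to the schedule of events.
3. **Section 11.4.4.** Report the number asked as the denominator for solicited events.
4. **Section 10.1.** Align with 8.1.2 by stating that the FBSE is required. Leave the rule that the investigator is informed immediately unchanged. The timing in item 1 already protects the blinding, so that safety step need not be loosened.

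If a form or the monitoring plan already contains such a question, a reference to it in 10.5 would serve in place of new wording, provided that it reaches everyone and records who was asked.

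The cost is one question at an existing visit and in an existing survey, one extra field, and short text changes, with no added visit. More mild events will be counted, and survey non-responders will remain unasked at day 42.

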## 10.6 REPORTING PROCEDURES

### 10.6.1 OHSU IRB REPORTING OF UNANTICIPATED PROBLEMS AND ADVERSE EVENTS

Unanticipated Problems (UP) and Adverse Events (AE) at the coordinating Study Site will be reported to OHSU IRB according to the policies, procedures and guidelines posted on the [OHSU IRB website](#).

Fatal and life-threatening UP will be reported to OHSU IRB no later than 7 days of notification of the event. All other UP reports will be submitted to OHSU IRB no later than 15 days of occurrence or notification of the event. Copies of the report documents will be kept on REDCap.

Unanticipated Problems and AEs at the satellite Study Site(s) will be reported to their respective IRB according to their respective policies, procedures and guidelines and to OHSU study Site members.

Events that must be reported by the Investigator to the IRB are detailed in the OHSU IRB **Investigator Guidance: Prompt Reporting Requirements (HRP-801)**. Events that meet the criteria for OHSU RNI must be reported to the IRB within 5 days of learning of the event. At a minimum, events requiring reporting to the IRB include:

- Any new or increased risk related to the research, including AEs or IND safety reports that require a change to the protocol or consent,
- New FDA black box warning,
- Publications identifying new risks,
- Data Safety Monitoring Board/Committee letters recommending changes or discussing new risks
- Unanticipated adverse device effect
- Unauthorized disclosure of confidential Participant information

### 10.6.2 CENTRAL REPORTING OF ADVERSE EVENTS FOR MULTI-SITE STUDIES

All Adverse Events (AE) should be reported as soon as possible but no later than 7 days of notification of the event. AEs should be reported to the respective Site's IRB accordance to their policies, procedures and guidelines and to OHSU study Site members.

### 10.6.3 FDA REPORTING

Some events must be reported to the FDA through the MedWatch Voluntary reporting program, even if the trial involves a commercially available agent. Events to be reported include any UPs and any SAEs with a suspected association to the Study intervention. An eligible person at the OHSU Coordinating Center will evaluate any reported UADE at the coordinating Study Site or satellite Study Site(s). The sponsor will provide to the FDA, all reviewing IRB's, and all sub-investigators an IDE Safety Report for any UADE that meets all of the following criteria: 1) an adverse effect caused by or associated with the device, 2) serious, and 3) Unanticipated. The sponsor will provide this no later than 10 working days after first notice of the effect. Thereafter, the sponsor will report any additional information concerning the effect per FDA request, and as warranted.

If the sponsor determines that the UADE presents an unreasonable risk to subjects, the sponsor will terminate all

investigations or parts of investigations that present risk as soon as possible (no later than 5 working days after the sponsor makes this determination), and no later than 15 working days after the sponsor first receives notice of the effect.

#### 10.6.4 SUSPECTED UNEXPECTED ADVERSE REACTIONS (SUSARS)

Per regulatory requirements, if an event is assessed by the Sponsor Institution as a Serious Unexpected Adverse Reaction (SUSAR), it is the responsibility of the Sponsor Institution to submit the SUSAR to Regulatory Authorities according to applicable regulations. In addition, the SUSAR will be distributed to the Investigators/Sites utilizing a Council for International Organizations of Medical Sciences (CIOMS) report form, or the MedWatch 3500A form). The Investigator will submit a copy of the report to their respective IRB or IEC per the governing institutional requirements and in compliance with local laws and guidelines.

#### 10.6.5 SKLIP INC REPORTING REQUIREMENTS

All events reported to the FDA will also be reported to Sklip Inc. as provided in the Research Agreement within 24 hours of reporting.

#### 10.6.6 REPORTING OF PREGNANCY

N/A

#### 10.7 STUDY STOPPING RULES

The overall Study will be paused and appropriate authorities notified if indicated by statistical stopping rules in this protocol.

### 11. STATISTICAL CONSIDERATIONS

#### 11.1 STATISTICAL AIM

The statistical aim of this pivotal trial is the estimation of diagnostic accuracy of the Sklip System estimated to pre-specified criteria: 95% sensitivity and 30% specificity for **Melanoma and atypical melanocytic nevi with uncertain malignant potential** (moderate, severe, and high grade atypia; those with pathology reports that include notes such as: borderline, cannot exclude melanoma, cannot exclude early evolving melanoma, unusual features, atypical spitz nevi, suspicion for melanoma, re-excision (or further removal) should be considered or is recommended in the pathologist management comment), 80% sensitivity and 30% specificity for **Squamous cell carcinoma**, 80% sensitivity and 30% specificity for **Basal cell carcinoma**.

#### 11.2 SAMPLE SIZE DETERMINATION

Sample size was calculated using formulas based on normal approximation to the binomial distribution. Previously recorded historical biopsy results for Melanoma, Squamous cell carcinoma, and Basal cell carcinoma across the proposed Study Sites averaged 2.3%, 12.5% and 29.2% of in-person dermatology Provider visits (i.e. cases), respectively. This represents disease prevalence rates in this pivotal Study target population of interest (i.e. patients who visited a Study Site within a 365 day period specifically for a mole spot check with concern for skin cancer, or a full body skin exam (FBSE) for the purpose of skin cancer prevention. This calculation presumes the exclusion of all other dermatology visits not related to a concern for skin cancer. Formulae (1) and (2) were used to estimate the sample size needed to evaluate the sensitivity (Se) and specificity (Sp), based on the diagnostic performance data available for melanoma from the SMSA Performance Study, and the target population case prevalence rates. The following values are inserted:  $Z_{\alpha/2} = 1.96$  for  $\alpha = 0.05$  level of significance, and  $d = 10\%$  margin of error for 95% Confidence Interval.

$$n_{Se} = \frac{Z_{\frac{\alpha}{2}}^2 \widehat{Se} (1 - \widehat{Se})}{d^2 \times \text{Prev}} \quad (1)$$

$$n_{Sp} = \frac{Z_{\frac{\alpha}{2}}^2 \widehat{Sp} (1 - \widehat{Sp})}{d^2 \times (1 - \text{Prev})} \quad (2)$$

Table 4 and Table 5 below summarizes the sample size estimates for cutaneous diseases of interest to evaluate the sensitivity and specificity of the investigational device (Sklip System). As can be seen from the table, the size estimate calculated using the sensitivity value for detecting melanoma (423 cases [lesions]) yields the largest number. The expected numbers of lesions that will be accordingly captured during the Study are summarized in Table 6.

Considering the larger number of cases required for evaluation of sensitivity (423 for Melanoma; based on SMSA performance of sensitivity for melanoma of 97.4%) as opposed to specificity (114 for SCC), a 49% specificity can be estimated from the hypothetical sample data. Previous peer-reviewed studies, exclusive to virtual visits, showed that participants submitted an average of 1.02 to 1.9 images per participant. Considering the aforementioned and average case submission rates reported by the proposed Study Sites, we expect a case submission rate of 1.5 per Study Participant. Assuming a 10% drop-out rate a total number of 310 Participants (dropout-inflated sample size) will be needed for the current study (310 = 423 ÷ 1.5 × 1.10).

**Table 4. Sample size estimates for cutaneous diseases of interest to evaluate the sensitivity of Sklip System based on the available target population prevalence data.**

Lesions	Sample Size Estimate to Test for Sensitivity											
	Melanoma			BCC			SCC			AMN		
	Confirmed	Excluded	Total	Confirmed	Excluded	Total	Confirmed	Excluded	Total	Confirmed	Excluded	Total
Suspicious	9	248	257	17	89	107	17	31	48	17	243	260
Non-Suspicious	1	165	166	1	38	39	1	13	14	1	104	105
Total Scanned	10	413	423	18	128	146	18	44	63	18	347	365
Prevalence	2.3%			12.5%			29.2%			5.0%		
Sensitivity	97.4%			95%			95%			95%		
Specificity	40%			30%			30%			30%		

The sample size was estimated using formulae (1) and (2) to test for sensitivity and specificity, respectively, with  $\alpha = 0.05$  significance level and 10% margin of error for 95% Confidence Interval. The respective sensitivity and specificity values were used to estimate the numbers of suspicious and non-suspicious lesions confirmed or excluded by the Ground Truth as described in the Sections above. BCC: Basal cell carcinoma, SCC: Squamous cell carcinoma, AMN: Atypical melanocytic nevi with uncertain malignant potential.

**Table 5.** Sample size estimates for cutaneous diseases of interest to evaluate the specificity of Sklip System based on the available target population prevalence data.

Sample Size Estimate to Test for Specificity											
Melanoma			BCC			SCC			AMN		
Confirmed	Excluded	Total	Confirmed	Excluded	Total	Confirmed	Excluded	Total	Confirmed	Excluded	Total
2	55	57	11	56	67	32	56	88	4	56	61
0	37	37	1	24	25	2	24	26	0	24	24
2	92	94	12	81	92	33	81	114	4	81	85
2.3%			12.5%			29.2%			5.0%		
97.4%			95%			95%			95%		
40%			30%			30%			30%		

The sample size was estimated using formulae (1) and (2) to test for sensitivity and specificity, respectively, with  $\alpha = 0.05$  significance level and 10% margin of error for 95% Confidence Interval. The respective sensitivity and specificity values were used to estimate the numbers of suspicious and non-suspicious lesions confirmed or excluded by the Ground Truth as described in the Sections above. BCC: Basal cell carcinoma, SCC: Squamous cell carcinoma, AMN: Atypical melanocytic nevi with uncertain malignant potential.

**Table 6.** Numbers of PSLCs expected to be captured in the estimated sample from the target population.

Lesions	Melanoma Confirmed	Melanoma Excluded	BCC	SCC	AMN	Total non- Melanoma Cancers	Total Malignant Lesions	Total Negative for Malignancy Lesions	Total
Suspicious	9	248	36	84	14	135	144	113	257
Non-Suspicious	0	165	15	36	6	58	58	107	166
Total	10	413	52	121	21	193	203	220	423
Prevalence	2.3%	97.7%	12.5%	29.2%	5.0%	46.7%	49.0%	51.0%	100%
Lesions per Melanoma	1	42	5	13	2	20	21	22	43

A review of all histologically confirmed Melanoma diagnosis made at OHSU within the past 10 years revealed over 3,500 cases. A review of all histologically confirmed non-Melanoma skin cancer diagnosis made at OHSU within the past 5 years revealed over 30,000 cases. Based off these findings, since three (3) additional Satellite Study Sites are each required to contribute at least fifteen (15) percent of the total sample size each, a maximum of 124 Participants at Site #1 OHSU (FDA suggested maximum enrollment cap of 40%) and a minimum of 47 participants (FDA suggested minimum enrollment of 15%) at each additional Site is feasible.

